PROTOCOL TITLE: Use of a computerized decision aid for prenatal aneuploidy screening

Short Title: Aneuploidy decision aid

Lead Investigator:

[name].

University of North Carolina at Chapel

Version Date: January 3, 2018

NCT number: 02991729

TABLE OF CONTENTS

Table of Contents	2
Abbreviations and Definitions of Terms	3
Protocol Synopsis	4
1 BACKGROUND AND RATIONALE	7
2 STUDY OBJECTIVES	9
3 INVESTIGATIONAL PLAN	10
4 STUDY PROCEDURES	12
5 STUDY EVALUATIONS AND MEASUREMENTS	14
6 STATISTICAL CONSIDERATIONS	15
10 DATA COLLECTION AND MANAGEMENT	17
14 REFERENCES	18

ABBREVIATIONS AND DEFINITIONS OF TERMS

Abbreviation	Definition
MSSKQ	Maternal serum screening knowledge questionnaire
cfDNA	Cell-free DNA screening

PROTOCOL SYNOPSIS

Study Title	Use of a Computerized Decision Aid for Prenatal Aneuploidy Screening
--------------------	--

Funder	
• National Center for Advancing Translational Sciences (NCATS), NIH, Grant #UL1TR001111• UNC Department of OBGYN Cefalo-Bowes Grant (internal funding)
---------------	---

Clinical Phase	Phase II
-----------------------	----------

Study Rationale	
• All women should be offered aneuploidy screening or testing in each pregnancy• Screening and testing options are complex• Decision aids have been shown to improve knowledge and decrease decisional conflict with healthcare decisions, including aneuploidy screening• Prior decision aids which have been evaluated for aneuploidy screening did not include the newest screening option of cell-free DNA
------------------------	---

Study Objective(s)	
Primary
 
• To evaluate whether use of the computerized decision aid is noninferior than an abbreviated visit with a genetic counselor in increasing patient knowledge 
Secondary
 
• To evaluate whether use of the computerized decision aid is noninferior than an abbreviated visit with a genetic counselor in
---------------------------	--

decreasing patient decisional conflict

- To evaluate whether use of the decision aid in addition to genetic counseling improves patient knowledge and decisional conflict over genetic counseling alone
- To examine test chosen for aneuploidy screening

Test Article(s)

(If Applicable)

A computerized decision aid was developed within a tablet-based application, available in Spanish and English, at a 10th grade reading level, to aid in patient education surrounding aneuploidy screening and testing options

Study Design

Unmasked randomized controlled trial

Subject Population

Inclusion Criteria

key criteria for Inclusion and Exclusion:

- English and Spanish-speaking pregnant women
- Undergoing genetic counseling for indication of aneuploidy screening
- Ages 18-50

Exclusion Criteria

1. Multiple gestation
2. Prior aneuploidy screening in current pregnancy
3. Prior abnormal ultrasound in current pregnancy

Number Of Subjects

200

Study Duration

Each subject's participation will last for the duration of the study visit (approximately 45 minutes).

The entire study is expected to last 12 months.

Study Phases

Screening (1) Screening: Women scheduled for genetic counseling for indication of aneuploidy screening will be approached regarding eligibility and willingness to participate prior to their scheduled appointment.

Study Treatment

Follow-Up (2) Intervention: Participants will be randomized either to use the above-described decision aid prior to genetic counseling or to genetic counseling alone.

(3) Follow-up: None after study visit

Efficacy Evaluations

(1) Knowledge: A 12 question modification of the MSSKQ questionnaire will be used to assess knowledge

(2) Decisional conflict: A validated low-literacy decisional conflict scale will be used to assess decisional conflict

Pharmacokinetic Evaluations N/A

Safety Evaluations N/A

Statistical And Analytic Plan

(1) Primary outcome: Noninferiority of knowledge will be assessed graphically and with Wilcoxon Rank-Sum

(2) Secondary outcomes: knowledge and decisional conflict scores will be assessed with Wilcoxon Rank-Sum

DATA AND SAFETY MONITORING PLAN Participants were provided with contact information for the PI should they have any concerns. No safety concerns are anticipated.

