Because low health literacy affects many women of reproductive age and because most obstetric providers have limited time in an initial prenatal visit to explain the rapidly expanding choice of tests, our aim was to develop a decision aid for aneuploidy screening and testing that could easily be used in various clinics and settings. Decision aids have been shown to improve patients' knowledge and decrease decisional conflict with health care decisions in healthcare settings,⁶ and in the field of obstetrics and gynecology.^{6,7} This is particularly true when decisions are complex and involve patient value assessment.⁶ A decision aid has been previously developed and tested to address aneuploidy screening,⁸ though an important new screening modality in cell-free DNA has become available since the development of this tool. We hypothesize that a computerized decision aid to review available aneuploidy screening and testing options would not be inferior to a counseling visit with a genetic counselor in increasing patient knowledge. The combination of the decision aid followed by a genetic counseling appointment would also be expected to decrease decisional conflict.

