2 STUDY OBJECTIVE

2.1 Primary Objective

The primary hypothesis of this study was that knowledge scores of women in group 2 following completion of the decision aid only would not be inferior to knowledge scores of women in group 1 following genetic counseling. A noninferiority limit of 1 question different on a 12 point questionnaire was selected as a clinically relevant difference.

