3 INVESTIGATIONAL PLAN

3.1 Study Design

This is an unblinded randomized controlled trial.

Women randomized to group 1 will meet with the genetic counselor as scheduled, then complete the knowledge and decisional conflict assessments. Women randomized to group 2 will self-administer the decision aid within the app, then complete the knowledge and decisional conflict assessments. Following this, they will meet with the genetic counselor as scheduled; following this appointment, they will again complete the same assessment. Additionally, prior to and following meeting with the genetic counselor, women in group 2 will be asked whether they would or did find it helpful to meet with a genetic counselor.

Genetic counselors will be educated prior to study initiation that their counseling should not be modified based on group assignment; generally, women < 35 years old received abbreviated counseling on aneuploidy screening and testing options and those \geq 35 years old received more extensive counseling. Within ACMG guidelines, all screening tests are available to all women; cost information and insurance coverage information on available tests will also be provided prior to final decision making. Women will then undergo their screening or testing modality of choice. All study participation and completion of initial screening will be completed within the single encounter.

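### The synopsis tests noninferiority against an abbreviated counseling visit, the body against genetic counseling as such, and the named test does not apply the 1-question limit

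*Combined protocol and SAP*

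**What the plan says.** **Comparator in the synopsis.** The primary objective is to show the aid "noninferior than an abbreviated visit with a genetic counselor in increasing patient knowledge". The secondary decisional-conflict objective uses the same comparator. The intervention entry under Study Phases drops the qualifier: women are randomized to the "decision aid prior to genetic counseling or to genetic counseling alone".

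**Comparator in the body.** Section 1 hypothesizes that the aid "would not be inferior to a counseling visit with a genetic counselor in increasing patient knowledge". Section 2.1 compares group 2 after the aid alone with "knowledge scores of women in group 1 following genetic counseling", and sets "A noninferiority limit of 1 question different on a 12 point questionnaire".

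**Counseling delivered.** Section 3.1 tells counselors not to vary counseling by arm. It then says that, generally, "women < 35 years old received abbreviated counseling on aneuploidy screening and testing options", while women at or above "35 years old received more extensive counseling". The synopsis admits women aged 18 to 50.

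**Analysis.** The synopsis states: "Noninferiority of knowledge will be assessed graphically and with Wilcoxon Rank-Sum". Section 6.2 compares the whole control group after counseling with the whole intervention group after the aid. It lists mean knowledge as the quantity and the rank-sum test as the method. Maternal age appears there only in the baseline comparisons.

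**The concern.** The same primary result permits different conclusions depending on which section is read. Someone relying on the synopsis would take a pass as evidence that the aid holds up against an abbreviated visit. Someone relying on section 2.1 would take it as evidence against counseling as these clinics deliver it. The two coincide only if all of group 1 receives what the synopsis calls abbreviated, and section 3.1 suggests that the older women generally receive more.

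A second gap affects either conclusion. The trial has a numerical limit of 1 question, but the plan does not say how that limit enters the analysis. Until it does, neither version of the objective has a decision rule.

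**Working it through.** **Inputs.** From the documents: limit 1 question (2.1); SD 3, 80% power, two-tailed alpha 0.05, 92 per arm, 7.5% fall-out, 100 per arm (6.1); counseling differs by age at 35 (3.1). Assumed, because the documents do not give them: the share of women aged 35 or older, the true differences by age group, and how much of the score variance age group explains.

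**1. The plan's own figures.** Fall-out: 92 / (1 - 0.075) = 99.5, rounded up to 100, which matches. Section 6.1 does not state the difference it was powered for. With the 1-question limit and no true difference, n per arm = 2 × 3² × (1.960 + 0.842)² / 1² = 141.3, so 142. The stated 92 is not reproduced. At SD 3 it corresponds to a difference of 3 × √(2/92) × (1.960 + 0.842) = 1.24 questions.

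**2. The comparator, place by place.**

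| Place | Comparator |
|---|---|
| Synopsis, primary and decisional-conflict objectives | abbreviated counselor visit |
| Synopsis, intervention entry | genetic counseling, no qualifier |
| Section 1 | counselor visit, no qualifier |
| Section 2.1 | group 1 after genetic counseling |
| Section 3.1, counseling delivered | generally abbreviated under 35, fuller at 35 or older |
| Section 6.2 | whole control group after genetic counseling |

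Only the two synopsis objectives carry the qualifier.

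**3. What a pooled result says about women who generally get abbreviated counseling.** Illustration only. With s the share aged 35 or older, pooled deficit = (1 - s) × deficit under 35 + s × deficit at 35 or older.

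| Assumed deficits | s = 25% | s = 50% | s = 75% |
|---|---|---|---|
| A: 1.5 under 35, 0 at 35 or older | 1.125 | 0.75 | 0.375 |
| B: 0 under 35, 1.5 at 35 or older | 0.375 | 0.75 | 1.125 |

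In A at 50% and 75% the pooled deficit is inside the limit although the younger group is outside it. In B at 75% the pooled deficit is outside although the younger group has none. The pooled figure therefore does not fix the abbreviated-visit answer in either direction.

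**4. Whether the named test applies the limit.** A rank-sum test of the two sets of scores tests for equal distributions. A nonsignificant result does not show that the deficit is below 1 question, and a significant one does not show that it exceeds 1. The test could apply the limit if one group's scores were shifted by 1 first, but neither the synopsis nor section 6.2 says so. The graphical assessment has no stated criterion.

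**5. What an interval would deliver at the planned size.**
- Standard error = 3 × √(2/92) = 0.442; 95% half-width = 1.96 × 0.442 = 0.87.
- Power against -1 with no true difference = Φ(1/0.442 - 1.96) = Φ(0.30) = 0.62.
- If age group explains an assumed 10% of variance, the half-width is 0.867 × √0.90 = 0.82. If it explains none, it stays at 0.87.
- Within one age group at an assumed 46 per arm, the half-width is 1.96 × 3 × √(2/46) = 1.23.

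**The case against.** The strongest reply is that this is a stray adjective. The hypothesis and the limit sit in section 2.1, the analysis in section 6.2 matches it, and no element of the design depends on the word. That stands: the issue is wording, and the randomized comparison is sound for the section 2.1 question.

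The adjective may also mean only that all study visits are short. The synopsis allows about 45 minutes for the whole visit and section 1.1 about 20 for the aid, leaving roughly 25 minutes in group 2 for questionnaires and counseling at any age. Section 3.1 does use the word in contrast to fuller counseling, but the term is undefined and the practice is described as general, so the documents do not settle which reading was meant.

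The illustration in the working rests on no trial data. It shows that a weighted average can differ from its parts. No section says the aid performs differently by age or counseling length, and scenario A needs the aid to do relatively worse against the shorter counseling. If fuller counseling never leaves a woman knowing less, a pooled pass would carry over to a hypothetical abbreviated visit for everyone. The documents do not state that assumption. It would still not settle the result in women under 35, and a pooled failure would not carry over.

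Finally, the missing limit in the test is separable from the comparator wording, and age adjustment is not required for validity. Both are true. They are raised together because both determine what the primary result can be said to show.

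**Conclusion.** The comparator is stated inconsistently, and the severity is minor. The pooled analysis answers for counseling as delivered and does not by itself support a claim about an abbreviated visit.

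A reader might infer more: that the control arm is the wrong one, that the comparison is biased, or that the pooled result would hide inferiority to the abbreviated visit. The documents support none of these. Section 2.1 asks about the control arm as it is, and counselors are told not to change practice by arm. The size and direction of any gap between the pooled and abbreviated-visit answers rest wholly on assumed values. Nor can it be said that the synopsis certainly means the counseling given to women under 35.

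The analytic consequence is firmer. As written, the rank-sum test does not apply the 1-question limit. The power of 62% and the requirement of 142 per arm rest on the plan's SD of 3, a 95% interval, a normal approximation and no true difference between groups.

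**What to change.** 1. **Wording.** Reconcile both synopsis objectives with sections 1, 2.1 and 3.1 by naming the comparator as genetic counseling as delivered, and state that no claim about an abbreviated visit will be drawn from the pooled result. This costs two edited sentences.
2. **Analysis.** In section 6.2 and the synopsis, base the noninferiority conclusion on the mean difference in knowledge (group 2 after the aid minus group 1 after counseling) with a 95% CI, adjusted for age group (under 35, 35 or older). Conclude noninferiority if the lower bound lies above -1. Age is already collected (section 5). This is a change of primary analysis and should be recorded as one. Adjustment may add little or no precision, and it does not isolate an abbreviated visit.
3. **Power.** Restate section 6.1 with the difference it assumes. At 92 per arm the rule above does not have the stated 80% power, so the team should either report the lower figure or revise the sample size.
4. **Optional.** Differences by age group with 95% CIs may be shown as descriptive only. They are wide and confounded with age, which the aid itself uses to tailor content (section 1.1). They therefore do not isolate counseling intensity and cannot confirm noninferiority.

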6.2 Statistical Methods

Baseline demographics

- Mean age - Wilcoxon rank sum
- AMA as categorical variable - chi2
- Race/ethnicity - Fisher exact
- Mean GA - Wilcoxon rank sum
- GA<14 wks as categorical - chi2
- Insurance status - Fisher exact
- Employed yes/no - chi2
- Education level - fisher exact
- Religion - Fisher exact
- Prior GC - chi2
- Planning invasive testing - Fishers exact
- Mean knowledge score on enrollment - Wilcoxon rank sum

Results

1. Compare control group following genetic counseling to intervention group following decision aid
 - Mean knowledge - Wilcoxon rank sum
 - Mean decisional conflict - Wilcoxon rank sum
 - Planned test - Fisher exact

2. Compare control group following genetic counseling to intervention group following decision aid and genetic counseling
 - Mean knowledge - Wilcoxon rank sum
 1. Represented in figure
 - Decisional conflict - Wilcoxon rank sum
 1. Represented in figure
 - Planned test - Fisher exact
3. Compare intervention group following decision aid to intervention group following both decision aid and genetic counseling
 - Mean knowledge - Wilcoxon signed rank
 1. Represented in figure
 - Decisional conflict - Wilcoxon signed rank
 1. Represented in figure
 - Planned test - descriptive (% changed)

No interim analyses are planned.

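### The synopsis sets a noninferiority objective for decisional conflict, but the plan gives no margin for it and only a rank-sum test of no difference, which cannot establish it

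*Combined protocol and SAP*

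**What the plan says.** The Protocol Synopsis opens its secondary objectives with "To evaluate whether use of the computerized decision aid is noninferior than an abbreviated visit with a genetic counselor in" and completes the sentence with "decreasing patient decisional conflict". The instrument is named there too: "A validated low-literacy decisional conflict scale will be used to assess decisional conflict". No score range, standard deviation or important difference is given for it.

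The single margin in the documents is in section 2.1: "A noninferiority limit of 1 question different on a 12 point questionnaire was selected as a clinically relevant difference". It concerns knowledge.

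For the analysis, the synopsis separates the two outcomes. For the primary it says "Noninferiority of knowledge will be assessed graphically and with Wilcoxon Rank-Sum". For the secondary outcomes it says only that "knowledge and decisional conflict scores will be assessed with Wilcoxon Rank-Sum". Section 6.2, Results 1, which compares the aid alone with counseling, lists "Mean decisional conflict - Wilcoxon rank sum" and nothing further for conflict. The figures planned in 6.2 belong to comparisons 2 and 3, not to this one.

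Elsewhere the noninferiority idea is narrower. The hypothesis at the end of section 1 is noninferiority for knowledge; for conflict it expects a reduction from the aid followed by counseling. Section 2.1 frames the noninferiority hypothesis on knowledge. Section 2.2 lists decisional conflict after the aid as a secondary outcome, with no noninferiority wording.

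**The concern.** A noninferiority conclusion requires rejecting the hypothesis that the aid is worse than counseling by at least a stated margin. The standard rank-sum test addresses a different hypothesis, that the two distributions are the same. Failing to reject it means only that a difference was not detected. For decisional conflict there is no margin, shifted null, confidence interval or decision rule, so the synopsis objective cannot be answered by the analysis attached to it.

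This is distinct from the similar weakness in the primary analysis. Knowledge has a margin, so an interval compared with 1 question would repair that analysis. The same repair is not available for conflict, because there is nothing to compare the interval with.

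At stake is how the aid-only comparison is reported. With a noninferiority objective on one page and only a difference test on another, a non-significant p-value could be taken as support for replacing the counselor visit as far as conflict is concerned.

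**Working it through.** **Inputs from the documents.** 92 evaluable women per arm, 80% power, two-tailed alpha 0.05, and a knowledge SD of 3 questions (section 6.1); a knowledge margin of 1 question (section 2.1). Nothing numerical is given for decisional conflict.

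**Assumptions.** Normal conflict scores with equal SD in both arms; differences expressed in SD units of the scale.

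**The plan's own figure.** No sample size is stated for conflict. The inflation in section 6.1 reproduces: 92 / (1 − 0.075) = 99.5, so 100 per arm. The 92 does not follow from an SD of 3 and a difference of 1, which give 2 × 3² × (1.960 + 0.842)² / 1² = 141.3, so 142 per arm. That is a separate matter for the primary outcome; here 92 is used only as the planned evaluable number.

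**Step 1. How often the planned test is non-significant when the aid is truly worse.** Simulated two-sided rank-sum test, 10,000 runs per setting:

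| True worsening | 92 per arm | 100 per arm |
|---|---|---|
| 0.2 SD | 75% | 73% |
| 0.3 SD | 49% | 46% |
| 1/3 SD | 40% | 36% |
| 0.4 SD | 25% | 22% |
| 0.5 SD | 9% | 7% |

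The 1/3 SD row is the knowledge margin in SD units (1 question / SD of 3). It is a yardstick borrowed from another instrument, not a margin for this one. If it were the margin, a rule based on the 95% confidence limit would wrongly declare noninferiority 2.5% of the time at that true difference. Reading non-significance as noninferiority would do so about 40% of the time.

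**Step 2. What an interval would give.** The standard error of a mean difference is √(2/92) = 0.147 SD. The 95% half-width is 1.96 × 0.147 = 0.29 SD.

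**Step 3. What margin the trial could support.** With a true difference of 0, one-sided alpha 0.025 and 80% power, the smallest margin is (1.960 + 0.842) × 0.147 = 0.41 SD. At a margin of 1/3 SD the power is Φ(0.333 / 0.147 − 1.96) = Φ(0.30), about 62%. The number needed per arm, 2 × (1.960 + 0.842)² / margin², is:

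| Margin | Needed per arm |
|---|---|
| 0.2 SD | 393 |
| 0.3 SD | 175 |
| 1/3 SD | 142 |
| 0.4 SD | 99 |
| 0.5 SD | 63 |

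**The case against.** The strongest reply is that noninferiority on conflict appears in one synopsis bullet only. Sections 1, 2.1 and 2.2 reserve it for knowledge, and the synopsis analysis plan attaches the word to knowledge alone. On that view the bullet is out of line with the body of the protocol, and the rank-sum test is an ordinary comparison of a secondary outcome. This largely stands, and it decides which remedy comes first. It does not remove the point, because the bullet is a stated objective and the documents disagree about what is being tested.

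Three stronger readings are tempting but not supported:

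- A reader might infer that the plan treats p > 0.05 as noninferiority. No section states how a non-significant result would be interpreted. The most that can be said is that the plan offers no other basis for the conclusion, so the misreading is possible.
- A reader might take the 75% and 49% at 0.2 and 0.3 SD as false-noninferiority rates. Such a rate exists only relative to a margin. On the 1/3 SD yardstick both shifts lie inside the margin, so calling them noninferior would be correct.
- A reader might add that a significant result could reflect a trivial difference. With 92 per arm, significance needs an observed difference of roughly 0.29 SD. Whether that is trivial cannot be judged without a margin, so the argument has little force here.

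It is also fair to say that this is a secondary outcome on which no sample size or stopping decision depends.

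**Conclusion.** The point holds in a limited form. The synopsis states a noninferiority objective for decisional conflict that sections 1, 2.1 and 2.2 do not share. No margin exists for it, and the only planned aid-only versus counseling analysis tests no difference. As written, the plan cannot establish that objective.

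The illustrative size is about 40% non-significant results at a true worsening of 1/3 SD and about 25% at 0.4 SD, assuming normal scores and 92 per arm. These show how little a non-significant p-value would say. They become error rates only once a margin is chosen, and the documents give neither a margin nor an SD for the scale. That the objective and the analysis do not match rests on the text alone and needs none of these assumptions. The matter should be corrected, but it does not bear on the primary outcome.

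**What to change.** - In section 6.2, Results 1, report for decisional conflict the group 2 minus group 1 difference (mean difference or Hodges-Lehmann shift) with a two-sided 95% confidence interval. The rank-sum p-value may accompany it.
- Reword the synopsis objective to estimating the difference in decisional conflict after the aid alone versus after counseling, which matches section 2.2.
- State that p > 0.05 is not evidence of noninferiority.
- Keep a noninferiority claim only if a justified margin in scale points can be fixed before any outcome data are examined. Judge it by the confidence limit on the side that means more conflict, and disclose the power limits from step 3. This condition may be hard to meet: the study is unblinded, and sections 4.1 and 4.2 already describe recruitment and assessments in the past tense.

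The cost is a few lines of wording and one interval, with no new data or participants. The downside is that a secondary claim becomes weaker.

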4.2 Intervention

Following informed consent, the app was accessed and a study ID assigned. Via a coin-flip algorithm within the app, women were randomly assigned to group 1 (control group) or group 2 (decision aid group). As it was not pragmatic for this study, randomization assignment was not blinded. Investigators were not involved in developing the randomization scheme within the app. All women completed an initial demographic and knowledge questionnaire immediately following randomization via self-administered assessments within the app.

Study flow is described in the below figure. Women randomized to group 1 met with the genetic counselor as scheduled, then completed the knowledge and decisional conflict assessments. Women randomized to group 2 self-administered the decision aid within the app, then completed the knowledge and decisional conflict assessments. Following this, they met with the genetic counselor as scheduled; following this appointment, they again completed the same assessment.

Additionally, prior to and following meeting with the genetic counselor, women in group 2 were asked whether they would or did find it helpful to meet with a genetic counselor.

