4.3 Subject Completion/ Withdrawal procedures

Participants are instructed to inform their enrolling research study personnel should they desire to withdraw and participation could be terminated at that time.

5 STUDY EVALUATIONS AND MEASUREMENTS (how measurements will be made)

- Demographic characteristics will be abstracted from questionnaires and medical chart
 - o Age
 - o Race/ethnicity
 - o Preferred language
 - o Parity
 - o Gestational age
 - o Site of enrollment
 - o Insurance status
 - o Employment status
 - o Education level
 - o History of genetic counseling in prior pregnancy
- Baseline knowledge assessment
 - o This will be assessed via the previously described modified MSSKQ questionnaire prior to intervention
- Knowledge and decisional conflict scores as described will be collected via self-administered questionnaires embedded within the application

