6 STATISTICAL CONSIDERATION

6.1 Sample size calculation

An initial power calculation was performed using historical data from the maternal serum screening questionnaire assuming a standard deviation of 3 questions; to achieve 80% power with a 2-tailed alpha of 0.05, 92 women would be needed in each arm. Assuming a 7.5% fall-out rate from women with nonviable pregnancies, 100 patients were required in each arm for a total enrollment of 200 women.

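### The primary claim is noninferiority within 1 question, but the planned analysis never uses that limit and gives no rule for declaring noninferiority

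*Combined protocol and SAP*

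**What the plan says.** - **Hypothesis (section 2.1).** Knowledge scores of group 2 "following completion of the decision aid only would not be inferior to knowledge scores of women in group 1 following genetic counseling".
- **Limit (section 2.1).** "A noninferiority limit of 1 question different on a 12 point questionnaire was selected as a clinically relevant difference". The limit appears nowhere else in the document.
- **Analysis (synopsis, Statistical and Analytic Plan).** "Noninferiority of knowledge will be assessed graphically and with Wilcoxon Rank-Sum". What is plotted is not described.
- **Analysis (section 6.2, Results item 1, the primary comparison).** "Mean knowledge - Wilcoxon rank sum". The note "Represented in figure" is attached to comparisons 2 and 3, not to this one.
- **Error rate and size (section 6.1).** With an assumed SD of 3 questions, "to achieve 80% power with a 2-tailed alpha of 0.05, 92 women would be needed in each arm". The limit is not mentioned.

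**The concern.** A noninferiority claim needs a result that rules out a deficit as large as the limit. That means an interval compared with the limit, or a test whose null hypothesis is a deficit of that size. The plan has neither. A standard rank-sum takes no difference as its null. A non-significant result may only reflect too little information. A significant result does not show whether the deficit is larger or smaller than 1 question.

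The document therefore does not say which result would establish its only primary claim. If non-significance were taken as success, the risk of accepting an aid that is a full question worse would be set by the spread of the scores, their closeness to the 12-point maximum and the number of women. It would not be set by the design. The trial is also unmasked, and section 7 gives the primary investigator access to the data for analysis, so a rule chosen after seeing results would be open to challenge.

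**Working it through.** **Inputs.** From section 2.1: limit 1 question. From section 6.1: SD 3, two-tailed alpha 0.05 (2.5% in the direction that matters for noninferiority), 92 per arm. Assumed, because the documents do not give them: group 1 mean scores from 6 to 11, and alternative SDs of 2 and 3.5.

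**The plan's own figure.** 2 × (1.960 + 0.842)² × 3² / 1² = 141.3, so 142 per arm, not 92. At SD 3, 92 per arm corresponds to a difference of 3 × 2.802 × √(2/92) = 1.24 questions, which the plan does not state. The fall-out step does reproduce: 92 / 0.925 = 99.5, so 100. The sample size is a separate point; 92 is used below because it is the planned number.

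**Non-significance read as noninferiority, continuous scores.** The true deficit is exactly 1 question.

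- Standard error at SD 3: 3 × √(2/92) = 0.4423. The deficit is 1 / 0.4423 = 2.261 standard errors.
- The rank-sum has efficiency 0.955 for normal scores: 2.261 × √0.955 = 2.21.
- P(not significant) ≈ Φ(1.96 − 2.21) = Φ(−0.25) = 0.40. Simulation (10,000 trials) gives 0.411.
- SD 2: Φ(1.96 − 3.31) = 0.09; simulated 0.088.
- SD 3.5: Φ(1.96 − 1.89) = 0.53; simulated 0.525.

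A smaller trial would do better under this reading. At 20 per arm and SD 3 the simulated rate is 83%.

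**Whole-number scores from 0 to 12.** Normal scores with latent SD 3 were rounded and clipped to 0–12, and group 2 was placed so that the realised mean deficit was exactly 1. There were 92 per arm and 10,000 trials per column. The last row adds 1 to every group 2 score and then applies a rank-sum.

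| Group 1 mean | 6 | 7 | 8 | 8.75 | 9.5 | 10 | 10.5 | 11 |
|---|---|---|---|---|---|---|---|---|
| False claim, non-significant rank-sum (%) | 36.3 | 35.8 | 34.6 | 30.3 | 24.9 | 19.4 | 12.9 | 5.3 |
| False claim, rank-sum after adding 1 (%) | 2.0 | 2.0 | 2.1 | 2.3 | 3.7 | 5.6 | 13.0 | 33.3 |

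Over the same means, the first row runs from 9.5% down to 0.9% at latent SD 2, and from 46.2% down to 9.1% at latent SD 3.5.

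**Mean difference with an unequal-variance 95% interval, success if the lower limit is above -1.** At a true deficit of 1, the false-claim rate is 2.3–2.7% for continuous scores and 2.15–2.80% over all 24 whole-number scenarios. Simulation error near 2.5% is √(0.025 × 0.975 / 10,000) = 0.16 percentage points. With 184 women split by coin flip, as section 3.2 plans, the rate is 2.2–2.6%. Adjusted for baseline knowledge (assumed latent correlation 0.5), it is 2.1–2.8%.

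**What that rule demands at 92 per arm and SD 3.** Half-width: 1.96 × 0.4423 = 0.867. The observed difference must exceed −1 + 0.867 = −0.133. With no true difference, the chance of success is Φ(2.261 − 1.96) = 0.618; simulated 0.608.

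**The case against.** The strongest defence is that the plan is brief rather than wrong. The synopsis names noninferiority as the thing assessed and promises a graph, and section 2.1 supplies the limit. The intended graph could be an estimate and interval drawn against it. A rank-sum can also be shifted by the limit or inverted to give an interval, and the absence of a figure note under item 1 of section 6.2 does not cancel the synopsis. That reading is possible, but no text states it. The synopsis names the same rank-sum for the secondary outcomes, and section 6.2 uses it for maternal and gestational age, so nothing marks its primary use as different.

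Several narrower points stand:

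- The error rates depend on a reading the plan does not state and on assumed means. They show that the error is uncontrolled; they do not estimate this trial's error. In one scenario (latent SD 2, mean 11) the rate is 0.9%, below 2.5%.
- A latent SD of 3 is not the score SD of 3 in section 6.1. After rounding and clipping, the realised group 1 SD falls from 2.90 to 1.63 as the mean rises, so the high-mean columns depart from the plan's input.
- A rank-sum shifted by 1 is valid at means of 6 to 8.75 (2.0–2.3%). The case against it rests on a possible ceiling, and the documents give no mean.

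None of these supplies the missing decision rule.

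**Conclusion.** The concern holds. Followed as written, the plan cannot establish its primary claim, because the limit never enters the decision. This should be settled before the primary result is interpreted.

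That conclusion comes from the text and needs no simulation. The size is conditional on non-significance being read as noninferiority at 92 per arm and a true deficit of exactly 1 question. It is about 41% at the plan's SD of 3 with continuous scores, and about 30–36% for whole-number scores with latent SD 3 and group 1 means of 6 to 8.75. The rate is lower near the ceiling. An interval compared with -1 keeps the rate close to 2.5% in every scenario examined.

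**What to change.** In the synopsis and in section 6.2, item 1:

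1. Define the primary analysis as the difference in mean knowledge score, group 2 after the decision aid minus group 1 after genetic counseling, with a two-sided 95% confidence interval (unequal-variance t).
2. Declare noninferiority only if the lower limit is above -1 question.
3. Define the graph as this estimate and interval with a reference line at -1.
4. State in advance whether the difference is adjusted for baseline knowledge. Both groups already provide it (section 4.2: "All women completed an initial demographic and knowledge questionnaire immediately following randomization"; section 5: "This will be assessed via the previously described modified MSSKQ questionnaire prior to intervention"). Because it is collected after an unblinded assignment, the plan should say why any adjustment is still acceptable.
5. Keep the rank-sum as supportive only. Do not make a rank-sum after adding 1 to group 2 scores the primary rule, since its error rises near the 12-point maximum.

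If outcome data have already been seen, label the rule as set afterwards.

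The change is wording and needs no new data. Its cost is that it exposes the limited power: about 62% at SD 3 with no true difference, against the stated 80%. That should be disclosed and dealt with as the separate sample-size point.
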